10.1 Analysis sets

10.1.1 Full Analysis Set

The Full Analysis Set (FAS) comprises all patients who received at least one dose of pasireotide s.c.

10.1.2 Safety Set

The safety set includes all patients who received at least one dose of pasireotide s.c. and had at least one post-baseline safety assessment.

Please note: the statement that a patient had no adverse events (on the Adverse Event CRF) constitutes a safety assessment.

10.2 Patient demographics/other baseline characteristics

Demographic and other baseline data (including disease characteristics) will be summarized descriptively for the FAS. Categorical data will be presented as frequencies and percentages. For continuous data, the mean, standard deviation, median, minimum, and maximum will be presented.

10.3 Treatments (study treatment, concomitant therapies, compliance)

Descriptive statistics will be used to summarize the mean daily dose and duration of pasireotide s.c. The actual and planned doses administered and reason for dose change will be listed.

Concomitant medications and significant non-drug therapies prior to and after the start of the study treatment will be summarized by ATC class and preferred term.

These analyses will be performed on the safety set.

10.4 Primary objective

Refer to [Section 3](#).

10.4.1 Variable

The primary variable is the proportion of patients having a drug-related adverse event that was recorded as grade 3 or 4, or as a serious adverse event.

The analysis of the primary variable is described in [Section 10.5.2.2](#).

10.4.2 Statistical hypothesis, model, and method of analysis

No statistical hypotheses are being tested in this study.

10.4.3 Handling of missing values/censoring/discontinuations

[figure not shown]
Not applicable. All attempts will be made to ensure that the database contains full information for all safety data.

10.4.4 Supportive analyses

Not applicable.

10.5 Secondary objectives

Refer to [Section 3](#).

10.5.1 Secondary efficacy variables

The secondary efficacy analysis will be performed on the FAS. Unless noted otherwise, missing values will not be imputed in these analyses. The parameters assessed at screening and not at baseline are to be considered as baseline.

10.5.1.1 Normalization of mean 24h-UFC at Week 12, 24 and 48

The number and percentage with corresponding exact two-sided 95% CI of patients achieving normalization of mean 24h-UFC (i.e. mean 24h-UFC \leq 1.0xULN) at Week 12, 24 and 48 (separately) will be presented.

If Week 24 mean 24h-UFC is missing then it will be imputed by the last available mean 24h-UFC of at least two samples between and including Week 12 and Week 24, and if Week 48 mean 24h-UFC is missing then it will be imputed by the last available mean 24h-UFC of at least two samples between and including Week 12 and Week 48. Summaries with and without imputing missing Week 24 and Week 48 mean 24h-UFC will be presented.

Similar analyses as defined above will also be performed at all other scheduled post-baseline assessments.

10.5.1.2 Reduction of mean 24h-UFC \geq 50% from baseline to Week 12, 24 and 48

The number and percentage with corresponding exact two-sided 95% CI of patients achieving a reduction of mean 24h-UFC \geq 50% from baseline to Week 12, 24 and 48 (separately) will be presented.

Similar analyses as defined above will also be performed at all other scheduled post-baseline assessments.

10.5.1.3 Change from baseline in mean 24h-UFC to Week 12, 24 and 48

Descriptive summaries of actual and percentage change with corresponding two-sided 95% CIs in mean 24h-UFC from baseline to Week 12, 24 and 48 will be provided.

Similar analyses as defined above will also be performed at all other scheduled post-baseline assessments.

10.5.1.4 Changes from baseline in GH and IGF-I to Week 12, 24 and 48

Descriptive summaries of actual and percentage change in mean GH and IGF-1 values from baseline to Week 12, 24 and 48 will be provided.

Similar analyses as defined above will also be performed at all other scheduled post-baseline assessments.

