4.9 Calculation of change

Baseline value is the value collected during the baseline assessment as per the specific definition applying to the parameter, e.g. lab value

Absolute change from baseline is the absolute difference between value at time point t (post-baseline) and value at baseline assessment, it is calculated as:

- $Absolute\ change\ from\ baseline = post-baseline\ value - baseline\ value$

Relative change from baseline, or Percentage change from baseline, is calculated as:

- $Relative\ change\ from\ baseline\ (\%) = (absolute\ change\ / baseline\ value) \times 100$

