4.12.1.2 CI for continuous variables

Two sided 95%Confidence Interval for continuous variable will be based on the t-distribution. The respective N, Mean and Standard error are outputted in to a data-step and then the TINV function is used to calculate the Confidence Interval as follows:

```
PROC MEANS DATA=test NOPRINT ;
  VAR age ;
  OUTPUT OUT=xxtmp N=n MEAN=mean STDERR=stderr ;
  RUN ;

  DATA xxtmp1 ; SET xxtmp ;
  lo = mean - ( TINV ( 0.95 , n-1 ) * stderr ) ;
  hi = mean + ( TINV ( 0.95 , n-1 ) * stderr ) ;
  RUN ;
```

5 Statistical methods and data analysis

Categorical data will be presented as frequencies and percentages. For continuous data, mean, standard deviation, median, minimum, and maximum will be presented.

A missing category for categorical data will be presented where applicable. Unless otherwise noted, percentages will be based on the number of patients in the relevant population or subgroup.

Whenever possible, minimum and maximum will be presented to the same precision as the raw data. Mean and median will be presented to one more decimal place and standard deviation to two more decimal places.

Unless noted otherwise, no imputation for missing data will be performed.

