In addition, descriptive summaries of actual and percentage change in mean 24h-UFC from baseline to Week 12, 24 and 48 and all other scheduled post-baseline assessments will be provided.

Changes from baseline to Week 12, 24 and 48 in clinical signs and symptoms

The following clinical signs (Table 5-1) of Cushing's disease will be assessed by descriptive summaries of the change in systolic BP (standing and sitting), diastolic BP (standing and sitting), BMI, waist circumference and weight from baseline to each post-baseline visit. In addition, the proportion of patients satisfying the clinically relevant thresholds specified in the following table will be calculated along with the exact two-sided 95% CIs at each scheduled post-baseline assessment.

Table 5-1 Clinical Signs

Clinical Sign	Unit, Scale	Clinically relevant threshold (at any time point)
Standing Systolic BP	mmHg	≤ 140 mmHg
Sitting Systolic BP	mmHg, mean of 3 assessments	mean of 3 assessments ≤ 140 mmHg
Standing Diastolic BP	mmHg	≤ 90 mmHg
Sitting Diastolic BP	mmHg, mean of 3 assessments	mean of 3 assessments ≤ 90 mmHg
BMI	kg/m ² , Class levels: < 25.0, 25.0 to < 30.0, ≥ 30.0	% of patients reducing by at least one class level
Waist circumference	cm	Reduction of ≥ 5% Reduction of ≥ 10%
Weight	Kg	Reduction of ≥ 5%

Similar analyses as defined above will also be performed at all other scheduled post-baseline assessments.

The following clinical signs and symptoms (Table 5-2) of Cushing's disease will be assessed by descriptive summaries of changes (or shifts) from baseline to each scheduled post-baseline assessment. The corresponding method of analysis for each clinical sign and symptom are provided in the table.

Table 5-2 Clinical Signs and Symptoms

Clinical signs and symptoms	Scale	Analyses Methods
Facial Rubor (redness)	0=none, 1=mild, 2=moderate, 3=severe	Investigator interpretation, Counts & shifts from baseline.
Hirsutism (Ferriman-Gallway scoring)	0=minimum, 36=maximum Scoring in females only	Investigator interpretation, Ferriman-Gallway score, Actual and % change from baseline
Supraclavicular fat pads	0=none, 1=mild, 2=moderate, 3=severe	Investigator interpretation, Counts & shifts from baseline.
Dorsal fat pads	0=none, 1=mild, 2=moderate, 3=severe	Investigator interpretation, Counts & shifts from baseline.

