. For example, if a patient answers all 12 items with 'Sometimes' or 'Somewhat', X = 36 and $Y = 100 \cdot 24/48 = 50$.

Similar analyses as defined above will also be performed at all other scheduled post-baseline assessments.

Changes from baseline to Week 12 , 24 and 48 in WPAI-GH scores

The WPAI-GH questionnaire is to assess work productivity and activity impairment.

WPAI outcomes are expressed as impairment percentages, with higher numbers indicating greater impairment and less productivity, i.e., worse outcomes, as follows (see [Reilly 2002](#)):

Questions:

- 1 = currently employed
- 2 = hours missed due to health problems
- 3 = hours missed other reasons
- 4 = hours actually worked
- 5 = degree health affected productivity while working
- 6 = degree health affected regular activities

Scores (multiply scores by 100 to express in percentages):

Percent work time missed due to health: $Q2/(Q2+Q4)$

Percent impairment while working due to health: $Q5/10$

Percent overall work impairment due to health:

$Q2/(Q2 + Q4)+[(1 - Q2/(Q2 + Q4)) \cdot (Q5/10)]$

[figure not shown]
Percent activity impairment due to health: $Q6/10$

Descriptive summaries of actual and percentage change in mean scores from baseline to Week 12, 24 and 48 will be provided. Similar analyses will also be performed at all other scheduled post-baseline assessments.

Changes from baseline in GH and IGF-I to Week 12, 24 and 48

Descriptive summaries of the absolute and relative change from baseline of GH and IGF-I at Week 12, 24 and 48 will be provided.

Similar analyses will also be performed at all other scheduled post-baseline assessments.

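### Percentage change in mean 24h-UFC gets its only interval from an arithmetic mean; adding a geometric mean ratio with a back-transformed CI would describe the typical fall better (minor)

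*Protocol*

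**What the plan says.** Protocol 10.5.1.3 commits to "Descriptive summaries of actual and percentage change with corresponding two-sided 95% CIs in mean 24h-UFC from baseline to Week 12, 24 and 48", and to similar summaries at the other scheduled visits. Mean 24h-UFC here is each patient's own average over two or three urine collections, so the percentage change is a per-patient figure. SAP 4.9 gives the definition: "Relative change from baseline, or Percentage change from baseline, is calculated as" the absolute change divided by baseline, times 100.

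The matching SAP 5.2.1 text plans "descriptive summaries of actual and percentage change in mean 24h-UFC" and names no interval. The interval therefore comes from the protocol commitment read with SAP 4.12.1.2: "Two sided 95%Confidence Interval for continuous variable will be based on the t-distribution". The code there takes the arithmetic mean plus or minus a t quantile times the standard error. SAP section 5 also lists mean, SD, median, minimum and maximum for continuous data. Neither document plans a log transformation, a geometric mean or an interval for the median.

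For GH and IGF-I the SAP plans "Descriptive summaries of the absolute and relative change from baseline of GH and IGF-I at Week 12, 24 and 48 will be provided". Neither the SAP nor the protocol attaches an interval to these.

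**The concern.** A percentage change can fall no lower than -100% but can rise without limit. If the post/baseline ratio is right-skewed, as ratios of positive measurements can be, the arithmetic mean of the percentages lies above the typical patient's value. A fall to half and a rise to double are opposite changes of equal size on the ratio scale, yet they average to (-50% + 100%)/2 = +25%.

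The only interval planned for relative change in UFC is centred on that mean. The median is shown without any measure of precision. In a study whose stated purpose is to document effects, the descriptive estimates and intervals are the product. A reader who takes the interval as the range for the typical percentage fall would read too small an effect, with more uncertainty than the data require.

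**Working it through.** **Inputs.** The plan has no figure to reproduce: no sample size calculation was done (Protocol 10.8, SAP 4.10.1), and no SD or skewness is given for UFC change. The documents supply the definition of percentage change (SAP 4.9), the interval method (SAP 4.12.1.2), the planned number of about 200 patients, and the statement in Protocol 1.2.1 that mean UFC fell by about 50% in the earlier Phase III study. Everything else is assumed: a lognormal post/baseline ratio with median m = 0.5 and SD of the log ratio s between 0.5 and 1.2.

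**Step 1: mean against typical change.** Typical change = 100(m - 1) = -50% for every s. Mean change = 100(m·exp(s²/2) - 1):

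- s = 0.5: 0.5 × exp(0.125) = 0.567, so -43.3%
- s = 0.6: 0.5 × exp(0.18) = 0.599, so -40.1%
- s = 0.8: 0.5 × exp(0.32) = 0.689, so -31.1%
- s = 1.0: 0.5 × exp(0.5) = 0.824, so -17.6%
- s = 1.2: 0.5 × exp(0.72) = 1.027, so +2.7%

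**Step 2: where the sign reverses.** m·exp(s²/2) > 1 requires s > √(2 ln 2) = 1.18. At that point the share of patients whose UFC rises is 1 - Φ(0.693/1.18), about 28%.

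**Step 3: the interval.** This step assumes 100 patients with data at a visit and uses 20,000 simulated samples with the 0.975 t quantile. The geometric-mean-ratio width follows from 100 × 0.5 × [exp(h) - exp(-h)] with h = 1.984·s/√100. For s = 1.0, h = 0.198 and the width is 50 × (1.219 - 0.820) = 20 points.

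| s | Mean change | Coverage of its own mean | Median width, t-interval (points) | Width, geometric mean ratio (points) |
|---|---|---|---|---|
| 0.6 | -40% | 94% | 15 | 12 |
| 0.8 | -31% | 93% | 24 | 16 |
| 1.0 | -18% | 91-92% | 38 | 20 |
| 1.2 | +3% | 90% | 59 | 24 |

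At n = 200, simulated coverage is 94.5% at s = 0.5, 92.4% at s = 1.0 and 91.2% at s = 1.2. The shortfall is modest and shrinks with n. The gap between mean and typical change in Step 1 does not depend on n.

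**Step 4: a different reading of the 50%.** The protocol's figure describes mean UFC, not the median of individual ratios. If 0.5 is taken as the mean ratio, mean change is -50% at every s and the median ratio is 0.5·exp(-s²/2). That gives 0.441 (-56%) at s = 0.5, 0.303 (-70%) at s = 1.0 and 0.243 (-76%) at s = 1.2. The sign never reverses, but the mean still understates the typical fall.

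**Step 5: a rough check on s.** Protocol 1.2.1 reports that UFC fell in 76% of patients in the 15-day proof-of-concept study. With m = 0.5 this implies s = 0.693/Φ⁻¹(0.76) = 0.693/0.706 = 0.98 and a mean change of about -19%. With assumed medians of 0.6 and 0.7, the implied s is 0.72 and 0.50, and the mean is about -22% and -21% against typical falls of 40% and 30%. This is only a plausibility check: the study was short and different, and lognormality is assumed.

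**The case against.** Several stronger readings are tempting, and the documents do not support them.

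- **That the typical fall is hidden.** It is not. The median, minimum and maximum are presented, and in the model above the median reads -50% in every scenario.
- **That this is the only interval bearing on UFC effect.** It is the only one for percentage change. Protocol 10.5.1.3 also promises an interval for actual change, to which the -100% floor does not apply. The proportion with at least a 50% fall has an exact interval; 50 of 100, for example, gives about 40% to 60%.
- **That a few large rises dominate or reverse the result.** No distribution is given. At s = 0.5 the shift is under 7 points, and reversal under this model needs about 28% of patients to rise, which is not a few. Withdrawal for lack of efficacy (Protocol 7.1.3.1) may also thin the upper tail at Weeks 24 and 48.
- **That the t-interval is wrong because it often misses -50%.** An interval for a mean is not meant to cover a median. The fair criticism is of the target, plus modest under-coverage.
- **That GH and IGF-I share the problem.** They have no planned interval, so the only issue there is a mean printed beside a median.

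It is also fair to say that the geometric mean ratio equals the typical change only if log ratios are roughly symmetric. In addition, UFC change is not a Table 3-1 endpoint, and no hypothesis is tested (Protocol 10.4.2).

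These arguments lower the stakes considerably. What they leave standing is that a responder proportion answers a threshold question, the median has no interval, and the interval on relative change sits on the summary most sensitive to skew.

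**Conclusion.** The point holds as a minor one. The sole interval for percentage change in mean 24h-UFC surrounds an arithmetic mean on a scale bounded below and open above. Under right skew that mean understates the typical fall, and its interval is wider than a ratio-scale one.

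With a lognormal ratio of median 0.5, the understatement is about 7 points at log-SD 0.5, 19 at 0.8 and 32 at 1.0 (from -43.3%, -31.1% and -17.6% against -50%). At n = 100 and log-SD 0.8 the interval is about 24 points wide against 16. These sizes rest on the assumed median, log-SD and lognormal shape, none of which the documents supply. The direction holds whether 0.5 is read as the median or the mean ratio. The effect is on the interpretation of a descriptive secondary analysis and not on any decision rule.

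**What to change.** In SAP 5.2.1, for mean 24h-UFC at Weeks 12, 24 and 48:

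- Take log(post/baseline) per patient and compute its mean with a two-sided 95% t-interval, using the 0.975 quantile.
- Back-transform, and report the geometric mean ratio as percentage change, 100 × (ratio - 1), with its interval.
- Name this as the main interval for relative change.
- Keep the arithmetic mean, median, minimum and maximum.

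The quantile needs stating because the SAP 4.12.1.2 code uses TINV(0.95, n-1), which is 1.653 at n = 200 instead of 1.972 and gives a 90% two-sided interval. That is a separate correction, but it falls in the same paragraph. The SAP 5.2.1 sentence should also carry the interval that the protocol promises.

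For GH and IGF-I the same summary is optional. It would need a stated rule for results below the limit of quantification, which SAP 5.3.3 currently leaves out of summary statistics.

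The cost is SAP wording and a few lines of code, with no new data. The downside is one more statistic to explain.

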10.5.1.5 Clinical signs and symptoms

The following clinical signs of Cushing's disease will be assessed by descriptive summaries of the change in systolic BP (standing and sitting), diastolic BP (standing and sitting), BMI, waist circumference and weight from baseline to each post-baseline visit. In addition, the proportion of patients satisfying the clinically relevant thresholds specified in the following

table will be calculated along with the exact two-sided 95% CIs at each scheduled post-baseline assessment.

Clinical signs	Unit, Scale	Clinically relevant threshold (at any timepoint)
Standing Systolic BP	mmHg	≤ 140 mmHg
Sitting Systolic BP	mmHg, mean of 3 assessments	mean of 3 assessments ≤ 140 mmHg
Standing Diastolic BP	mmHg	≤ 90 mmHg
Sitting Diastolic BP	mmHg, mean of 3 assessments	mean of 3 assessments ≤ 90 mmHg
BMI	kg/m ² , Class levels: < 25.0, 25.0 to < 30.0, ≥ 30.0	% of patients reducing by at least one class level
Waist circumference	cm	Reduction of ≥ 5% Reducing of ≥ 10%
Weight	Kg	Reducing of ≥ 5%

The following clinical signs and symptoms of Cushing's disease will be assessed by descriptive summaries of changes and shifts from baseline to each scheduled post-baseline assessment. The clinical signs and symptoms that will be analyzed and the corresponding methods of analyses are provided in the following table.

Clinical signs and symptoms	Scale	Analyses methods
Facial Rubor (redness)	0=none, 1=mild, 2=moderate, 3=severe	Investigator interpretation, Counts & shifts from baseline.
Hirsutism (Ferriman-Gallway scoring)	0=minimum, 36=maximum Scoring in females only	Investigator interpretation, Ferriman-Gallway score, Actual and % change from baseline
Supraclavicular fat pads	0=none, 1=mild, 2=moderate, 3=severe	Investigator interpretation, Counts & shifts from baseline.
Dorsal fat pads	0=none, 1=mild, 2=moderate, 3=severe	Investigator interpretation, Counts & shifts from baseline.
Muscle strength	0= able to stand easily with arms extended, 1 = able to stand after several efforts without using arms as assistance, 2=able to stand only by using arms as assistance 3= completely unable to stand	Direct observation of ability to stand unaided. Counts & shifts from baseline.
Striae	0=none, 1=mild, 2=moderate, 3=severe	Investigator interpretation, Counts & shifts from baseline.
Bruising	0=none, 1=mild, 2=moderate, 3=severe	Investigator interpretation, Counts & shifts from baseline.

10.5.2 Safety objectives

10.5.2.1 Analysis set and grouping for the analyses

For all safety analyses, the safety set will be used.

The overall observation period will be divided into three mutually exclusive segments:

1. Pre-treatment period: from day of patient's informed consent to the day before first dose of study medication,
2. On-treatment period: from day of first dose of study medication to 28 days after last dose of study medication
3. Post-treatment period: starting at 29 days after last dose of study medication

10.5.2.2 Adverse events (AEs)

The definition of an adverse event for this study can be found in [Section 8.1](#).

Summary tables for adverse events (AEs) will include only AEs that started or worsened during the on-treatment period, the **treatment-emergent** AEs. However, all safety data (including those from the pre and post-treatment periods) will be listed and those collected during the pre and post-treatment period will be flagged.

For the primary objective of the study, the number and percentage of patients having any drug-related adverse event that was recorded as a grade 3 or 4, or as a serious adverse event will be summarized by system organ class and/or preferred term, severity (based on CTCAE grades), type of adverse event and relation to study treatment.

In addition, the incidence of treatment-emergent adverse events (new or worsening from baseline) will be summarized by system organ class and/or preferred term, severity (based on CTCAE grades), type of adverse event and relation to study treatment. Deaths will be listed and summarized by cause of death.

10.5.2.3 Laboratory abnormalities

The summaries will include all laboratory assessments collected no later than 28 days after study treatment discontinuation. All laboratory data will be listed and those collected later than 28 days after study treatment discontinuation will be flagged in the listings.

For laboratory tests covered by the Common Terminology Criteria for Adverse Events (CTCAE) version 3.0, the study's biostatistics and reporting team will grade laboratory data accordingly. For laboratory tests covered by CTCAE, a Grade 0 will be assigned for all non-missing values not graded as 1 or higher. Grade 5 will not be used. In the unlikely case when a laboratory normal range overlaps into the higher (i.e. non-zero) CTC grade, the laboratory value will still be taken as within normal limits and assigned a CTC grade of zero.

For laboratory tests where grades are not defined by CTCAE, results will be graded by the low/normal/high classifications based on laboratory normal ranges. The following summaries will be produced for the laboratory data (by laboratory parameter):

- Shift tables using CTCAE grades to compare baseline to the worst on-treatment value,

- For laboratory tests where CTCAE grades are not defined, shift tables using the low/normal/high classification to compare baseline to the worst on-treatment value,
- Shift tables of fasting glucose and related biochemical parameters using the ADA (2010) or similar low/normal/high classifications to compare baseline to the worst and last on-treatment value.

The following listings will be produced for the laboratory data:

- Listing of patients with laboratory values outside the laboratory reference ranges with values flagged to show the corresponding CTC grades and the classifications relative to the laboratory reference ranges,
- Listing of all laboratory data with values flagged to show the corresponding CTCAE grades and the classifications relative to the laboratory normal ranges.

